8. REGULATORY ISSUES

8.1. ETHICS APPROVAL

The Study has obtained approval from the London-Central Research Ethics Committee (REC) and Health Regulator Authority (HRA).

8.2. CONSENT

Participants interested in taking part will register their interest on the Ipsos MORI web portal and give separate consent to participate in the study, **for** subsequent data linkage on outcomes and willingness to be contacted about any future interventional research. At registration, young persons aged 12-15 years will be additionally asked to provide consent from their named parent / guardian, with the LFIA then posted to that parent / guardian.

8.3. CONFIDENTIALITY AND DATA PROTECTION

The Chief Investigator will hold the overall responsibility of preserving the confidentiality of participants taking part in the study from the Sponsor.

Section 251 of the NHS Act 2006 will be used as the basis for sharing patient identifiable data (PID) without prior consent. Approval for Section 251 support was granted by the Confidentiality Advisory Group at the Health Research Authority.

Ipsos MORI

All personal data will be held securely in line with ISO27001 Information Security Standard and in accordance with data protection policies.

NDRS

All data will be held securely in accordance with NHS Digital's data security standards and the National Congenital Anomaly and Rare Disease Registration Service's (NCARDRS') confidentiality policy. These are in line with ISO27001.

NHSBT

All data will be held securely in accordance with the NHSBT's Information Security and Confidentiality and Data Protection policies. These follow the principles of ISO27001. NHSBT's ICO Data protection registration Number is Z9210360.

At the end of the study, Ipsos MORI will delete all personal data relating specifically to this study from their systems (i.e. exclusively obtained via study procedures). NHSBT and NDRS will hold data for up to 10 years

8.4. INDEMNITY

Imperial College London holds negligent harm and non-negligent harm insurance policies which apply to this study.

8.5. SPONSOR

Imperial College London will act as the Sponsor for this study.

8.6. FUNDING

The Medical Research Council are funding this study [MR/W029200/1], in collaboration with health charities (Kidney research UK, Blood Cancer UK, Vasculitis UK and the Cystic Fibrosis Trust).

8.7. AUDITS

The study may be subject to audit by Imperial College London under their remit as sponsor and other regulatory bodies to ensure adherence to GCP and the UK Policy Frame Work for Health and Social Care Research.

9. STUDY MANAGEMENT

The day-to-day management of the study will be co-ordinated through NHSBT CTU. A study management group will be convened to provide ongoing oversight of operational activity.

10. PUBLICATION POLICY

The study management group will be involved in reviewing drafts of the manuscripts, abstracts, press releases and any other publications arising from the study. Any publications arising will also be approved by funders. Authors will acknowledge that the study funding as detailed in Section 8.6 above. Authorship will be determined in accordance with the ICMJE guidelines and other contributors will be acknowledged.

12. SUMMARY OF CHANGES

Version	Author	Date	Reason for revision
2.1	[name] [name]	07.12.2021	To adjust endpoint to at least 21 days post 3 rd vaccine and take into account Government notification of 4 th doses for clinically vulnerable people.

			
 1. Outcome measures: Study Summary, page 6 and Eligibility p7 2. 4th dose in Background Section 1.1, p13 3. New Study Objective listed in section 2, p 14 4. New Outcome Measure re 4th dose added and outcome 1 updated to at least 90 days Section 3.1, p 15 5. Addition to Research Plan, Section 4.1, page 14 6. Additions to the Statistics and Data Analysis listed in Section 7, pages 20 and 21. 7. Data Flow diagram on page 10 updated to include Date of Birth 8. Data Flow diagram on page 9 to include NHSBT data flow process akin to NDRS 9. Trial coordinator details added to page 2
3.3	[name] [name] [name]	15/02/2022	
 • Page 7- Eligibility - Addition of Immunosuppressed young adults aged 12 to 17 years • Page 14 – Amended to Adults and young people ≥ 12 years • Page 14 NHSBT Cohort – amended to Any adult or young person ≥ 12 • Page 15 NDRS cohort – amended to adults or young people ≥ 12 years • Page 16 - To re-test adult transplant recipients who have completed MELODY study participation following their third vaccine dose, after receipt of their fourth dose. • Page 21 - young persons aged 12-15 years will be additionally asked to provide consent from their named parent / guardian • Page 26 – 3 additional references Nos 4 - 6

13. APPENDIX 1. REPRODUCIBILITY AND STATISTICAL DESIGN ANNEX

This is an observational cohort study which will recruit 12,000 participants to each of 3 patient populations - 36,000 in total. We anticipate a LFIA result return rate of 85%, giving data on 10,200 cases in each participant population. Participants will either be invited at random to participate (autoimmune and cancer), or sign-up themselves (transplant), minimising potential recruitment bias, although self-selection bias could occur for either approach. This can be assessed by comparing those recruited against wider data on the registries participating in the study, and risk adjustment for any important confounders associated with outcome will be conducted.

LFIA diagnostic accuracy.

The lateral flow device to be used is the Fortress COVID-19 Total Antibody Device for the detection of IgM and IgG SARS-CoV-2 against the spike protein. The device has been evaluated for use in detecting anti-S in transplant patients and found to have a sensitivity of 92% and specificity of 95%¹³. The sample size calculation is described previously. The event rate of freedom from infection at 6 months in the group with antibodies was estimated from data in the PHE report "COVID-19 vaccine surveillance report - week 37". Table 2 of this report presents case rates per 100,000 for those who have received 2 doses of vaccine, which we have taken as our best estimate for event rates in a group with SARS-CoV-2 antibodies. The age-adjusted mean event rate from this data shows a 0.79% infection rate over a 4 week period in August 2021. Multiplying this up for our 6-month (180 day) follow-up period would suggest an event rate of 5.08%. However, this data relates to the UK population at large, not the higher risk immunosuppressed population that will be recruited to MELODY. Recent data on COVID-19 infection among those with rare autoimmune rheumatic disease showed that the age-standardised infection rate in this group was 1.54 times higher than in the general population¹⁷. We have therefore inflated our anticipated event rate by 50% to give the final event rate of 7.62% for this group (freedom from infection rate of 92.4%). Using the same process for the PHE data on unvaccinated individuals would suggest an infection rate 2.12% higher in the group with no SARS-CoV-2 antibodies. We have therefore powered the study to detect a 2% difference between those with and without antibodies. The statistical design and analysis was developed with co-applicants [name], [name] and [name].

1. JCVI advice on the UK vaccine response to the Omicron variant.
2. Kamar, N., et al. Assessment of 4 Doses of SARS-CoV-2 Messenger RNA-Based Vaccine in Recipients of a Solid Organ Transplant. *JAMA network open* **4**, e2136030 (2021).

3. Caillard, S., *et al.* Antibody response to a fourth mRNA Covid-19 vaccine boost in weak responder kidney transplant recipients. *medRxiv*, 2021.2009.2003.21262691 (2021).
4. Qin, C.X., *et al.* Antibody response to 2-dose SARS-CoV-2 mRNA vaccination in pediatric solid organ transplant recipients. *American Journal of Transplantation* **22**, 669-672 (2022).

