1.2. RATIONALE FOR CURRENT STUDY

Effective protection and management strategies of SARS-CoV-2 infection in immunocompromised adults have wide-reaching implications. For example, evidence has shown; a) they are more likely to have severe disease, which is associated with morbidity and mortality¹⁴⁻¹⁷; b) they are more likely to have prolonged infection, and viral shedding¹⁸; c) they are a risk for promoting viral evolution and escape mutations¹⁹.

Immunocompromised young persons (aged 12-17 years old) are also considered to be at heightened risk from SARS-CoV-2 infection. Recent studies have suggested that this group mounts stronger responses following SARS-CoV-2 vaccination than are observed in vaccinated immunosuppressed adults, but numbers of participants were small, and the Joint Committee on Vaccination and Immunisation (JCVI) has recommended that the immunocompromised young also should receive a booster vaccine following three primary vaccines⁴⁻⁶. Clarification of how this group respond to SARS-CoV-2 vaccination will inform future immunisation strategies.

The aim of this proposal is to assess at a population level; 1) the proportion of immunosuppressed people who have detectable SARS-CoV-2 antibodies following at least 3 vaccine doses, and the sociodemographic, disease, and treatment characteristics that influence antibody status; 2) if the detection of antibodies inversely correlates with subsequent risk of SARS-CoV2 infection and/or severity of disease in immunosuppressed individuals.

We aim to target patient groups least likely to mount an immune response to vaccination^{1,2,9}: a) solid organ transplant recipients; b) patients with a rare autoimmune disease; c) patients with haematological malignancies, specifically lymphoid malignancies. We will use comprehensive registries to identify and recruit patients

from these groups, and utilise the existing linkages these registries already have to obtain COVID-19 outcome information.

We hypothesise that a sizeable proportion of immunosuppressed people will have no detectable SARS-CoV-2 antibodies following either their third or fourth vaccine dose, and that this cohort is particularly susceptible to SARS-CoV-2 infection and death.

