4.3. RECRUITMENT

To ensure study start time is aligned with vaccine roll out, recruitment of transplant participants (via NHSBT) will differ from cancer and autoimmune participants. This is a pragmatic decision based on differences in patient identifiable data recorded by the transplant and NDRS registries. The recruitment plans for the different cohorts are outlined below. Those wishing to participate in the study will register via a web portal developed by Ipsos MORI, as per REACT-2. They will consent electronically for participation in the study, subsequent data linkage on outcomes and willingness to be contacted about any future interventional research.

Participate information sheets will be available for all potential recruits, both paper and electronic access, depending on method of recruitment.

People with solid organ transplants: Transplant recipients will be invited to join the study by self-registration via the study web portal. Eligibility for transplant recipients will be assessed by them providing their NHS/CHI number and year of most recent transplant at the time of opting-in to the study. This will be immediately verified against the data held by the UK Transplant Registry before the patient proceeds to register for the study.

Participants will be invited to join ('opt-in' method) via communications via the British Transplant Society, NHSBT, transplant centres, patient charities and social media. Linkage to the NHSBT and NHS Digital registries will provide confirmation that the applicant is a solid organ transplant recipient and details of their vaccine status. Young transplant recipients (aged 12-15) will be additionally asked for their parent / guardian details upon registering on the study web portal.

Simultaneous application for access to NHS Digital will be made. If the target number of 12,000 participants is not reached via the opt-in methods by the time approvals are obtained, invitations will be sent out to a random sample of patients on the transplant registry akin to the patients on the NDRS databases below. Baseline participant characteristics of all participants on the transplant registry are available and will enable a description of the study participants in relation to the whole registry.

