As of 14th February 2022, 2,500 adult solid organ transplant recipients have self-registered with the trial web portal and returned the results of the LFIA they received following their 3rd vaccine dose. Depending on availability of LFIA kits, participants who had an initial negative test will be further invited to perform an additional LFIA test, after receipt of their fourth or subsequent vaccine dose. These additional tests will provide data on the proportion of transplant recipients who seroconvert after their fourth or subsequent vaccine dose, despite being negative for anti-SARS-CoV-2 IgG antibodies after their third dose.

People with cancer and autoimmune disease: A random selection of eligible patients with autoimmune disease or haematological malignancy registered on the NCARDRS and NCRAS databases respectively, will be invited to join the study via personalised letter. Up to 2 reminders will be sent to potential participants. Patients responding to the invitation will register via the Ipsos MORI web portal. Using the experience from REACT-2, we estimate a response rate of 70% at registration and 85% at lateral flow test completion.

Following registration on the web portal and completion of a short online questionnaire including information on immunosuppression and medical history, sociodemographic variables and COVID-19-related behaviours and COVID-19 infection history, participants will be sent a LFIA test, which is provided with a detailed instruction booklet and link to an instruction video. For consenting young persons aged 12-15, the LFIA kit will be addressed to the parent / guardian whose name they have provided. Participants will be asked to carry out the test and follow the instructions to read the result and to take a photograph of the completed test, if possible. They will then provide their results via the web portal. A telephone helpline will be established to deal with any queries that may arise. Usability of the test has been assessed in REACT-2 study.

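### As specified, no step in the plan corrects the transplant cohort's headline antibody proportions for self-selection, and the stated ±0.91% makes no allowance for it

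*Combined protocol and SAP*

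**What the plan says.** **Target.** Section 1.2: "The aim of this proposal is to assess at a population level", starting with the proportion who have detectable antibodies. Section 1.1 says the results could help estimate how many patients might benefit from other forms of prophylaxis.

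**Transplant recruitment.** Section 4.3: "Participants will be invited to join ('opt-in' method) via communications via the British Transplant Society, NHSBT, transplant centres, patient charities and social media". If this has not reached 12,000 by the time data-access approvals arrive, a random sample of the transplant registry will be invited. By 14 February 2022, 2,500 adult recipients had self-registered and returned a result.

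**Handling of selection.** Appendix 1 says participants are invited at random or "sign-up themselves (transplant), minimising potential recruitment bias, although self-selection bias could occur for either approach". It then proposes to check recruits against the wider registry data, and adds: "risk adjustment for any important confounders associated with outcome will be conducted". Section 4.3 says registry baseline data "will enable a description of the study participants in relation to the whole registry".

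**Analysis.** Section 7, items 1 and 2, report the proportions with and without antibodies after the third and fourth doses, with 95% CIs. A general sentence adjusts all outcomes for known risk factors where appropriate. No weighting, post-stratification or standardisation is named. The sample-size text gives ±0.91% for a proportion of about one third with 10,200 results, and ±0.97% at 50%.

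**Other cohorts.** Section 4.3, for the randomly invited cohorts: "we estimate a response rate of 70% at registration and 85% at lateral flow test completion". Section 4.2 says autoimmune sampling begins with patients given Rituximab in the previous two years.

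**The concern.** An opt-in sample reached through centres, charities and social media is not a probability sample of the registry. Section 1.1 itself supplies reasons why joining could be related to antibody status. It says response depends on disease, immunosuppression and vaccine type, and that many patients still shield out of anxiety that vaccination has not worked for them.

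The remedies named serve other purposes. A comparison with the registry detects imbalance but does not change the estimate. Risk adjustment for confounders serves the comparisons and associations in items 3 to 5. A marginal proportion in items 1 and 2 still averages over whoever took part unless it is explicitly standardised to a stated population.

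What is at stake is the study's headline figure. Any difference between participants and eligible registry patients in organ, age, treatment or motive passes straight into the proportion reported as lacking antibodies. A reader given an interval of under one point either side would take that figure as settled for the population.

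**Working it through.** **1. The plan's own figure (section 7, sample size).** Inputs: n = 0.85 × 12,000 = 10,200; p about 1/3. Half-width = 1.96 × √[p(1−p)/n].
- p = 1/3: 0.915 points; p = 0.33: 0.913 points (stated 0.91).
- p = 0.5: 0.970 points (stated 0.97).

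Both figures reproduce. The formula is that for a simple random sample and contains no term for selection.

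**2. Illustration: a difference in recorded mix.** The shares and the 50% rate are assumptions; the documents give none. Suppose one group is 50% antibody-negative and makes up 20% of participants, and the overall proportion among participants is 1/3.
- Rate in the remainder: (1/3 − 0.2 × 0.5)/0.8 = 29.17%.
- Group is 30% of the eligible registry: 0.3 × 0.5 + 0.7 × 0.2917 = 35.4%, so the unweighted figure is 2.1 points too low.
- Group is 40%: 0.4 × 0.5 + 0.6 × 0.2917 = 37.5%, so it is 4.2 points too low.

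Reversing the imbalance would reverse the sign.

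**3. Cost of weighting in the same illustration.** Design effect = Σ (sample share × weight²), with weight = registry share / sample share.
- 30% case: 0.2 × 1.5² + 0.8 × 0.875² = 1.0625. Half-width = 1.96 × √[1.0625 × 0.354 × 0.646/10,200] = about 0.96 points.
- 40% case: 0.2 × 2² + 0.8 × 0.75² = 1.25. Half-width = 1.96 × √[1.25 × 0.375 × 0.625/10,200] = about 1.05 points.

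**4. How little selection matches the half-width.** Let antibody-negative people take part at r times the rate of antibody-positive people (r is assumed), with true p = 1/3. The observed proportion is q = pr/(pr + 1 − p). Coverage of the nominal 95% CI is by normal approximation.

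| r | q | Bias (points) | Coverage |
|---|---|---|---|
| 0.90 | 31.0% | −2.3 | 0.1% |
| 0.95 | 32.2% | −1.1 | 31% |
| 1.05 | 34.4% | +1.1 | 36% |
| 1.10 | 35.5% | +2.1 | 0.5% |

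The bias equals 0.91 points at r of about 0.96 or 1.04. This r is total selection; weighting removes only the part explained by recorded factors.

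**5. How far recruitment had gone.** 2,500/10,200 = 24.5% of the expected transplant results had come by opt-in at the date given. The final split between routes is not known.

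**6. The other two cohorts.** 0.70 × 0.85 = 59.5% of invitees are expected to give a result, so random invitation does not remove self-selection there either.

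**The case against.** The plan is not blind to the problem. Appendix 1 concedes self-selection under either route and plans a registry comparison. Section 7, item 5, gives antibody rates by clinical and sociodemographic factor, from which a reader with the registry mix could re-standardise on one factor at a time. Section 7 also calls itself high-level and defers some detail to an SAP that is not in the document reviewed, so weighting may be specified there. These points stand. They limit the finding to what the document specifies, but they do not supply a corrected headline estimate.

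Three stronger readings are tempting and are not supported.
- **That the cohort is simply volunteers.** Section 4.3 commits to random invitation if opt-in falls short, and with 24.5% of results in hand that share could be substantial.
- **That risk adjustment cannot correct the proportions.** Section 7 adjusts all outcomes where appropriate, and a model standardised to the eligible registry would correct for measured mix. What can be said is that no such standardisation is specified.
- **That the interval is wrong.** The ±0.91% is a precision figure for participants and is correct as sampling error. The fault would lie in reading it as a population interval that covers selection.

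It is also fair that the illustrative mix has no source in the documents. It shows how error arises, not how much there is.

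**Conclusion.** The concern holds in a limited form. The transplant cohort is recruited by opt-in first, with random invitation as a conditional supplement, and the statement that sign-up minimises recruitment bias has no support in the document. The steps named do not, as specified, correct the marginal proportions that answer the first aim.

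The size and direction of the bias cannot be derived from the documents. Under the assumed mixes it is 2.1 to 4.2 points, more than twice the stated half-width. A relative difference in participation of about 4% by antibody status would already match that half-width. The conclusion rests on the aim being a population-level proportion and on the absence of weighting or standardisation from the text reviewed. It does not show that the eventual estimate will be materially wrong.

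**What to change.** **Transplant cohort, items 1 and 2.** Beside the unweighted proportion, report one weighted or standardised to the eligible registry population: aged 12 or over, with a functioning transplant, and with the number of vaccine doses that each item requires. The whole registry is the wrong target, because it includes people outside these criteria. Use recorded registry and vaccine variables such as organ, age, sex, time since transplant and vaccine type, plus ethnicity and region if held. Give a CI that reflects the weights.

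**Recruitment route.** If random invitation is used, report the proportions separately for opt-in and invited participants, as a direct check on volunteer bias.

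**Autoimmune and cancer cohorts.** Use non-response weights built from each cohort's own variables. In the autoimmune cohort, also account for the sampling that starts with Rituximab-treated patients.

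**Wording.** State that the CI excludes residual selection on unrecorded factors such as shielding or anxiety. Replace the Appendix 1 claim that the recruitment routes minimise recruitment bias with a plain statement that self-selection is possible under each.

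**Cost.** SAP wording and a modest analysis. Section 4.3 says registry baseline data are available, though which variables they include needs confirming. The interval becomes slightly wider, and only recorded characteristics are corrected for.
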